#### **7.4.6 Center Variability**

Treatment effect could vary due to different patient mixes between the treating hospitals. We will investigate, at least for the primary endpoints and first secondary endpoints for short and long-term outcomes, the possible dependence of treatment effect on treatment hospital. First, we will describe treatment effects without the use of any baseline covariates, and then we will include hospital effects in our models used in the original analyses. We will perform further exploratory analyses as indicated by the data.

## 8 SAFETY AND ADVERSE EVENTS

### 8.1 Definitions

#### 8.1.1 Adverse Event

An adverse event (AE) is defined as any untoward medical occurrence in a patient or clinical investigation subject administered an investigational product which does not necessarily have a causal relationship with this treatment. An adverse event can therefore be any unfavorable and unintended sign (including an abnormal laboratory finding, for example), symptom, or disease temporally associated with the use of an investigational product or protocol specified procedure, whether considered related to the product or protocol specified procedure. Any worsening (i.e., any clinically significant adverse change in frequency and/or intensity) of a preexisting condition that is temporarily associated with the use of the Sponsor's product, is also an adverse event. Sponsor's product includes any pharmaceutical product, biological product, device, diagnostic agent or protocol-specified procedure, whether investigational (including placebo or active comparator medication) or marketed, manufactured by, licensed by, provided by or distributed by the Sponsor for human use.

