## 2 STUDY OBJECTIVES

The purpose of this Phase IIb clinical study is to evaluate the efficacy and safety of autologous UCB-MNC intramyocardial injections into the single, morphological right ventricle of subjects with HLHS or HLHS variants requiring Stage II surgical repair. Thirty to fifty treated subjects and thirty to fifty control subjects will be accrued. Subjects accrued in the treatment arm (Arm A) of this study will be treated with a single dose following successful completion of Stage II surgical repair. Subjects accrued in the control arm (Arm B) of this study will be followed according to the same protocol requirements as the treatment arm but will not receive cell therapy. In the treatment and control arms, surrogate markers of cardiac function, growth, success in reaching Stage III surgical repair pre-operative work-up, time to cardiac transplantation or death, and cumulative days of hospitalization will be recorded and evaluated following the completion of Stage II surgery for up to four years, or until the pre-operative work-up for the Stage III surgical repair has been completed or until cardiac transplant, whichever is first. Development and quality of life as measured by questionnaires will also be monitored. Follow-up surrogate markers and the other variables noted above that are recorded for this study will be compared to baseline and by study arm. The surrogate markers and other variables are described in Section 3 of this protocol.

The objective is to evaluate the short-term (up through 3 months post-Stage II surgical repair) cardiac function, growth, and cumulative days of hospitalization following discharge for the Stage II surgical repair in the treatment and control arms, adjusting for baseline.

This evaluation will also include long-term (6 months and up to 4 years post-Stage II surgical repair or until the pre-operative work-up for the Stage III surgical repair has been completed or until cardiac transplant), cardiac function, growth, ability to reach Stage III surgical repair pre-operative work-up and time to cardiac transplantation or death in the treatment and control arms, adjusting for baseline.

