#### **7.4.5 Safety Analysis**

Adverse Events (AEs) will be described by count and frequency, by body system and severity and groups compared using the chi-square test.

The long-term endpoint regarding arrhythmia events and arrhythmia medication will be analyzed regarding safety. Additional adverse events which will be separated out for analyses of their own will be occurrences of bleeding, to such an extent they would be regarded as AEs, decreased cardiac function, and tumor formation.

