#### 8.1.2 Serious Adverse Event

A serious adverse event is any adverse event occurring during any use of Sponsor's product that:

- Results in death;
- Is life threatening;
- Results in persistent or significant disability/incapacity;
- Results in or prolongs an existing inpatient hospitalization;
- Is an important medical event based upon appropriate medical judgement; it may jeopardize the subject, or it may require intervention to prevent one of the other outcomes listed in the above definitions.

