## **8.3 Medical History/Preexisting Conditions**

Medical history will be recorded once consent is obtained. Any new findings/abnormalities identified prior to enrollment will continue to be recorded as medical history.

A preexisting condition is one that is present prior to enrollment. A preexisting condition will be recorded as an adverse event only if the frequency, severity and/or the character of the condition worsens after enrollment and the event meets the definition of an adverse event as described in this protocol.

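### The AE and SAE definitions are worded around use of the product and do not fit the untreated control arm, so the planned between-arm AE comparison could be biased toward apparent harm from the cells

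*Combined protocol and SAP*

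**What the plan says.** **Definitions.** Section 8.1.1 opens with "any untoward medical occurrence in a patient or clinical investigation subject administered an investigational product". Its second sentence is wider and takes in signs, symptoms or disease "temporally associated with the use of an investigational product or protocol specified procedure", whether or not considered related. Worsening of a preexisting condition has its own clause: a clinically significant adverse change "that is temporarily associated with the use of the Sponsor's product, is also an adverse event". The section then states that "Sponsor's product includes any pharmaceutical product, biological product, device, diagnostic agent or protocol-specified procedure", qualified as items made, licensed, provided or distributed by the Sponsor. Section 8.1.2 defines an SAE as "any adverse event occurring during any use of Sponsor's product" that meets a seriousness criterion.

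**Link back to the definition.** Under Section 8.3 a preexisting condition becomes an AE only if it "worsens after enrollment and the event meets the definition of an adverse event as described in this protocol". Section 4.7 sends new or worsening conditions that lead to medication changes to Section 8.

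**Collection.** Section 4.3 enrolls both arms at the Procedural Timeout. Footnote 8 of Section 6.5 starts AE assessment at enrollment. Section 6.2 records new or worsening symptoms after enrollment, and Section 8.4 requires active questioning at every contact. None of these is limited to one arm.

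**Control arm and analysis.** Section 2 says Arm B "will be followed according to the same protocol requirements as the treatment arm but will not receive cell therapy". Section 7.2 puts all controls with follow-up data in the safety population. Section 7.4.5 describes AEs by body system and severity, with "groups compared using the chi-square test".

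**The concern.** A between-arm comparison of event frequencies is interpretable only if the same event in the same child would be recorded in either arm. An Arm A child meets the opening sentence of 8.1.1 throughout follow-up, because the product has been given. An Arm B child never meets it and must qualify through the procedure wording. The site knows the arm, so a doubtful case need not be resolved the same way on both sides.

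Any resulting loss falls on Arm B and makes the cells look harmful. Section 1.4 describes a population with frequent expected events arising from surgery and from the underlying disease. Interim safety results go to the DSMB (7.4.1), whose reviews inform continued enrollment in both arms (Section 1). A distorted comparison could therefore affect conduct of the study as well as the final report.

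**Working it through.** **Step 1. The plan's own figures.** The documents give no AE rate and no power for AEs. The only power figures are in Section 7.1: effect size 0.57 with 50 per arm, and 0.74 with 40% attrition (50 × 0.6 = 30 per arm). Solving the two-sample t-test for 80% power at two-sided alpha 0.05 gives 0.566 and 0.736, so both reproduce. A one-sided test at those effect sizes would have about 89% power, so the plan's alpha is two-sided. Section 7.4.5 states no level; two-sided 0.05 is carried over as an assumption.

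**Step 2. Three kinds of Arm B event read against the text.**

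| Arm B event | Opening sentence of 8.1.1 | Procedure wording | Result |
|---|---|---|---|
| Arrhythmia during the Stage II hospital stay | Not met | Met: telemetry runs from enrollment to discharge or up to 30 days (6.2.1), exams and vitals are daily (6.2.2), and Stage II surgery is a row in the 6.5 schedule | AE |
| Complication of a study blood draw | Not met | Met | AE |
| Worsening heart failure with readmission at month 5 | Not met | Doubtful: the 3-month clinic visit and 6-month phone visit have ±14-day windows, so no scheduled procedure is near | Ambiguous |

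In the third row, 8.3 requires the definition to be met. The worsening clause asks for use of the Sponsor's product, and the provided-by-the-Sponsor qualifier fits site-performed care poorly. Section 8.2 would make the readmission serious, but only if it is already an AE. Section 8.4, the 6-month AE assessment and, if medication changes, Section 4.7 all point toward recording it. Two readings are open. In Arm A the same event meets the opening sentence.

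**Step 3. What lost capture would do to one comparison.** Assumptions, none given in the documents: the same true proportion p of children with an event in both arms; all captured in Arm A; a fraction c captured in Arm B; uncorrected chi-square on children with at least one event.

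With a ~ Binomial(n, p) in Arm A and b ~ Binomial(n, pc) in Arm B,

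z = [(a − b)/n] / √[2·p̄(1 − p̄)/n], where p̄ = (a + b)/(2n).

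The probability of a false excess in Arm A is the exact sum over all (a, b) with z > 1.96.

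| n per arm | p | c = 1 | c = 0.9 | c = 0.75 | c = 0.5 |
|---|---|---|---|---|---|
| 50 | 0.2 | 2.6% | 4.6% | 10.1% | 30.2% |
| 50 | 0.5 | 2.8% | 8.0% | 25.5% | 74.5% |
| 50 | 0.7 | 2.5% | 11.0% | 44.3% | 95.5% |
| 30 | 0.2 | 2.4% | 3.8% | 7.2% | 19.3% |
| 30 | 0.5 | 2.6% | 6.0% | 16.3% | 51.6% |

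Hand check at n = 50, p = 0.5, c = 0.75, by normal approximation. The recorded proportions are 0.500 and 0.375, so p̄ = 0.4375. The null standard error is √(2 × 0.4375 × 0.5625/50) = 0.0992, and the actual one is √[(0.25 + 0.2344)/50] = 0.0984. Then (0.125 − 1.96 × 0.0992)/0.0984 = −0.71, giving a probability of 24%, against 25.5% exact.

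**The case against.** The strongest reply is that Arm B events will be recorded anyway, and much of it stands. Section 8.1.1 needs only temporal association with a protocol-specified procedure, and such procedures are counted within the Sponsor's product. The 6.5 schedule marks cell delivery and the Study Timeout as Arm A only but does not so mark AE assessment. Section 8.8 records moderate-or-worse AEs regardless of relatedness, and Section 8.2 makes AEs that lead to hospitalization serious with no during-use condition. The authors evidently meant an arm-neutral rule.

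Two stronger readings are therefore tempting but unsupported:

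- A reader might infer that the definitions capture almost nothing in Arm B, so the comparison is bound to show false harm. That takes the opening sentence of 8.1.1 alone. The procedure wording and the collection rules contradict it, and no passage shows how much capture is lost.
- A reader might infer that the during-use phrase in 8.1.2 removes every event after the injection from SAE reporting. Section 8.11 deals with events up to 30 days after cell therapy. Section 1.4 says this protocol was used to report the Phase I data, including 27 SAEs, 22 of them (15 + 7) in two children with a prolonged course. The phrase has not been applied that way, though it remains poor wording for a definition that governs 24-hour reporting.

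The reply does not remove the conflict. Sections 4.7, 8.2, 8.3 and 8.8 all start from the term that 8.1 defines, so they cannot repair the definition. It is also unsettled whether Stage II surgery counts as protocol-specified: Section 1.4 calls it standard of care, and it is complete before enrollment.

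A separate asymmetry in 8.8 is not cured by redefining AEs: the relatedness criterion admits mild, non-serious events only in Arm A.

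**Conclusion.** The concern holds as a conflict between the definitions and the collection rules, with a possible bias in a known direction. It is clearest for worsening of underlying disease after the post-operative period. It is weak for in-hospital events, which the procedure wording reaches in both arms.

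The size is conditional. At full Arm B capture the false-excess rate is nominal (about 2.5% in that direction). At 50 per arm and capture of 90%, it is 5% to 11% for true incidences of 0.2 to 0.7. Only a substantial loss makes a false signal likely. Incidence and capture are both assumed. The figures apply to a single comparison, whereas 7.4.5 plans several by body system and severity, with incidence and capture differing by category. No sample size or power figure in the plan is affected.

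**What to change.** - **8.1.1:** define an AE as any untoward medical occurrence, or worsening of a pre-existing condition, from enrollment (the Procedural Timeout) onward in a subject in either arm, whether or not related to the product or a study procedure. This replaces the product-based opening and the worsening clause, including the apparent slip of temporarily for temporally.
- **8.1.2:** replace "any adverse event occurring during any use of Sponsor's product" with: any adverse event occurring from enrollment to the end of study participation, in either arm.
- **8.1.3 and 8.1.5:** keep product-related wording here only, where it belongs.

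Sections 4.7, 8.2, 8.3 and 8.8 then inherit an arm-neutral definition without further edits. The cost is a short protocol amendment, a memo to sites and somewhat more recording in Arm B, which the 7.4.5 comparison needs.

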#### 8.1.2 Serious Adverse Event

A serious adverse event is any adverse event occurring during any use of Sponsor's product that:

- Results in death;
- Is life threatening;
- Results in persistent or significant disability/incapacity;
- Results in or prolongs an existing inpatient hospitalization;
- Is an important medical event based upon appropriate medical judgement; it may jeopardize the subject, or it may require intervention to prevent one of the other outcomes listed in the above definitions.

#### 8.1.3 Suspected Adverse Reaction

Any adverse event for which there is a reasonable possibility that the cell therapy product or cell delivery procedure caused the adverse event will be considered a suspected adverse reaction.

#### 8.1.4 Unexpected Adverse Event

An adverse event is considered unexpected if it is not listed in the Investigator's Brochure or the study protocol, or if it has occurred at a greater severity or specificity than is listed in the Investigator's Brochure or the study protocol.

#### 8.1.5 Serious and Unexpected Suspected Adverse Reaction (SUSAR)

An adverse event is considered a SUSAR if it is serious AND unexpected AND is a suspected adverse reaction per the definitions above.

## **8.2 Hospitalization, Prolonged Hospitalization or Surgery**

Any adverse event that results in hospitalization or prolonged hospitalization, or results in in-patient ( $\geq 24$  hours) surgery (e.g., pacemaker generator replacement) will be recorded as a serious adverse event.

## **8.3 Medical History/Preexisting Conditions**

Medical history will be recorded once consent is obtained. Any new findings/abnormalities identified prior to enrollment will continue to be recorded as medical history.

A preexisting condition is one that is present prior to enrollment. A preexisting condition will be recorded as an adverse event only if the frequency, severity and/or the character of the condition worsens after enrollment and the event meets the definition of an adverse event as described in this protocol.

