#### **4.3 Enrollment/Procedural Timeout**

Enrollment in either arm of this study will occur at the Procedural Timeout. The Procedural Timeout will be conducted in the operating room, by a trained site investigator, following the completion of the Stage II repair. During the Procedural Timeout, a site investigator will confirm all inclusion and exclusion criteria have been met per Section 4.1 of this protocol and document his/her decision to enroll the subject. If the site investigator determines that the subject, in either arm, fails to meet all inclusion and exclusion criteria, the subject will be declared a screen failure (see Section 4.5) and exited from the study. A subject should not be enrolled in either arm of the study if the subject has surgical complications during the Stage II repair that result in, or could be reasonably expected to result in, significantly decreased cardiac function.

For the treatment group, if a subject is determined to be eligible to enroll, the Procedural Timeout will also include confirmation that the subject's identity matches the patient identifiers on the investigational product label, confirmation of the number of injection sites and product volume to be delivered, and confirmation that there aren't any anticipated complications or concerns.

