### **6.1.3 Stage II Surgery:**

- Changes in Medical History
- Changes in Concomitant Medications
- Physical Exam (including weight)
- Vital Signs (temperature, heart rate, blood pressure, oxygen saturation)

Any new findings/abnormalities identified prior to enrollment will continue to be recorded as medical history unless considered related to a study-related test or procedure.

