 3 Tests/procedures will be performed daily during the hospitalization starting on Day 0. Continuous telemetry is not required on day of hospital discharge.  
 4 Laboratory tests, 12-lead ECG, and echo should be completed within 3 days of the discharge date. However, the laboratory tests, 12-lead ECG, and echo don't have to be repeated if the discharge date changes unexpectedly due to non-cardiac related issues.

- 5 To be conducted at 6 months post-Stage II surgery and every 6 months following the 12 month in-clinic visit for up to 4 years or until pre-operative Stage III work up or cardiac transplant.
- 6 Data to be collected from standard of care Stage III surgery pre-op work up in subject's medical records.
- 7 A subject will be considered enrolled on the study after completion of the procedural time-out.
- 8 Collection of medical history to occur up to enrollment. AE assessments to begin immediately following enrollment.
- 9 During Stage II Surgery hospital stay, changes in concomitant medications will not be recorded.
- 10 Includes weight, except for during post-op hospital stay
- 11 Includes temperature, heart rate, blood pressure and oxygen saturation. Temperature not required at 3 or 12-month in clinic visit.
- 12 Includes the following tests: High Sensitivity Troponin T, CRP, and NT-proBNP. On day 0, only the cardiac biomarker panel (High Sensitivity Troponin T) will be collected at 3 hr  $\pm$  30 min and 6 hr  $\pm$  30 min after enrollment.
- 13 Includes the following tests: RBC, WBC, Hemoglobin, Hematocrit, Platelets, Neutrophils, Lymphocytes, Monocytes, Eosinophils and Basophils
- 14 Includes the following tests: ALT, ALP, AST, Total Bilirubin, Albumin, Total Protein, BUN, and Creatinine.
- 15 Cardiac MRI will only be required at baseline. It is not required at 3 month visit or 12-month follow up. Baseline cardiac MRI should occur within 60 days prior to Stage II surgery.
- 16 When clinically available.
- 17 Questionnaires will be administered to participants at baseline and at 12, 24, 36 and 48 months post Stage II surgery for the duration of a subject's participation in the study.
- 18 Treatment arm only. Must occur within 5 days prior to cell delivery (see Sect. 6.1.2).
- 19 Required for both treatment and control arms (see Sect. 4.3).

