## 8.6 Causality

Causality of AEs should be assessed using the following relatedness categories:

- Definitely related: the event is *clearly* related the cell therapy product or its delivery procedure
- Probably related: the event is *likely* related the cell therapy product or its delivery procedure
- Possibly related: the event *may be* related the cell therapy product or its delivery procedure
- Unlikely related: the event is *doubtfully* related the cell therapy product or its delivery procedure
- Not Related: the event is *clearly not* related the cell therapy product or its delivery procedure

Adverse events that are unrelated to the cell therapy product or its delivery procedure, but are related to study-required tests and/or procedures, must also be specifically assessed.

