## **8.10 Expected Events**

The following are events that may occur as a result of receiving the cell product:

- Mild ventricular tachycardia and/or other mild ventricular arrhythmias
- Mild myocarditis
- Mild pericarditis
- Mild to moderate myocardial infarction
- Mild to moderate pericardial effusion(s)
- Mild to moderate fever for up to 3 days following cell delivery
- Mild to moderate bleeding at the injection site

There are no long-term adverse effects associated with an MRI. There are some potential side effects associated with the general anesthesia required to complete the MRI examination. Most of these are very mild and will go away shortly after the anesthesia care is stopped. The mild side effects include nausea, dizziness, and headache. Other potential risks include, but are not limited to, adverse medication reactions (allergies, etc.), abnormal heart rhythms, low blood pressure or impaired breathing. These more serious problems are very rare, affecting less than 1 in 2000 children.

The risks associated with a Transthoracic Echocardiogram (TTE) include the possibility of mild discomfort associated with placement of the ultrasound transducer on the chest wall while acquiring the echo images. The risks associated with a TTE using moderate (conscious) sedation include possible prolonged sedation, nausea, vomiting and/or a slight risk of allergic reaction. There are no long-term adverse effects associated with the echocardiogram itself.

Repeated or lengthy use of general anesthetic and sedation drugs during surgeries or procedures in children younger than 3 years may affect their brain development.

Intravenous access catheters may be placed as part of sedation/anesthesia for the echoes and MRIs. Placing an IV may cause some pain and bleeding or bruising at the spot where the needle enters the body. Rarely, it may cause fainting. The longer an IV catheter is left in place, the more common it is for redness or infection to develop.

There may be data privacy risks pertaining to the collection of patient data for any study, including this study.

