### **Patient Preparation**

- Magnetic resonance safety screening by MR personnel.
- Measure and document subject height (cm) and weight (kg) if not already performed during this visit.
- Obtain intravenous access, if not already performed, preferably in upper extremities. May need one cannula in each arm if patient has bilateral SVC/Glenn.
- General anesthesia is given.
- Transfer subject to the MR scanner.
- Attach ECG leads for cardiac gating (ensure that gating is good once in the scanner)

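### Section 8.3 files every pre-enrollment finding as medical history while 6.1.3 exempts findings caused by study procedures, so a complication of the baseline research MRI under general anesthesia can escape adverse event grading and reporting

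*Combined protocol and SAP*

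**What the plan says.** **When enrollment happens.** Section 4.3 places enrollment, in both arms, at the Procedural Timeout in the operating room once the Stage II repair is complete. Everything in the baseline work-up of 6.1.1 is therefore done in screening.

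**What is done in screening.** Schedule note 15 reads "Cardiac MRI will only be required at baseline". Appendix C, under Patient Preparation, calls for intravenous access and states "General anesthesia is given". Section 8.10 acknowledges the risk: "There are some potential side effects associated with the general anesthesia required to complete the MRI examination". Section 6.1.1 lets a clinical MRI from the 60 days before surgery stand in for the research scan.

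**How earlier findings are classified.** Section 8.3: "Any new findings/abnormalities identified prior to enrollment will continue to be recorded as medical history". Section 6.1.3 gives the same rule with an exception: such findings "will continue to be recorded as medical history unless considered related to a study-related test or procedure". The second paragraph of 8.3 adds that a condition already present before enrollment becomes an AE only if it worsens afterwards.

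**When AE assessment starts.** Schedule note 8: "AE assessments to begin immediately following enrollment". The schedule marks no AE assessment at consent, baseline or surgery, and 6.2.1 likewise records AEs from enrollment onward.

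**What the safety chapter asks for.** Section 8.1.1 includes events tied to a protocol procedure in the AE definition. Section 8.6 says that AEs which are not due to the product or its delivery but "are related to study-required tests and/or procedures, must also be specifically assessed".

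**Loss of eligibility.** If a child fails the criteria at the Timeout, "the subject will be declared a screen failure (see Section 4.5) and exited from the study". Section 7.2 restricts analysis to consented, eligible subjects and bases the safety analysis on treated children and controls with follow-up.

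**The concern.** The protocol adds a risk of its own in screening and names it, but its timing rules put that risk before AE collection. A site that works from 8.3 and the schedule would enter an anesthesia complication of the research MRI as history. It would then get no severity, seriousness or causality assessment and start no 24-hour SAE report. A site that works from 6.1.3 and 8.6 would treat the same event as an AE. Classification of research-procedure harm would then depend on which section the site read, in both arms.

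Screen failures are the sharper case. A screening complication can itself cost a child eligibility, for instance under exclusion 6a (an urgent or unplanned intervention shortly before surgery) or 6c (an investigator's prediction of a poor outcome). Those children leave the study and the analysis set together.

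**Working it through.** The point rests on comparing the text. The plan gives no count of such events to reproduce.

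**Step 1. Follow one hypothetical event.** A child has low blood pressure needing intervention during a research-only baseline MRI.

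| Provision | What it does with the event |
|---|---|
| 8.1.1 | It is an AE, being associated with a protocol procedure |
| 8.6 | It must be assessed; no start date or form is given |
| 6.1.3 | It is not left as medical history; no form or timeline is given |
| 8.3, first paragraph | It is medical history, with no exception |
| 8.3, second paragraph | It is an AE only if it worsens after enrollment |
| Schedule, note 8 and 6.2.1 | No AE assessment takes place yet |
| 8.8 | If serious, or moderate or worse, it would go on the AE eCRF; if serious, within 24 hours |

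Sections 8.1.1, 8.6 and 6.1.3 point to capture. Section 8.3 and the schedule point to medical history. No provision says which prevails or where a pre-enrollment AE is entered.

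**Step 2. Suppose the child then loses eligibility.** By 4.3 and 6.2.1 the child is a screen failure. By 4.5 the failure is documented in the eCRF, but AE recording is not mentioned. By 7.2 the child is in no analysis set. This holds even at a site that applies 6.1.3 correctly.

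**Step 3. Check the recording threshold.** Section 8.8 records an AE if it is serious, if it is at least possibly related to the study drug or its delivery, or if it is moderate or worse. Relatedness to a study test is not a trigger. A mild, non-serious effect of the MRI or anesthesia would therefore not reach the eCRF after enrollment either.

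**Step 4. Size.** Section 8.10 puts the more serious anesthesia problems at under 1 in 2000 children, so take p = 1/2000 = 0.0005 as an upper bound. With one research scan per child and N children:

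- expected events = N × p
- chance of at least one = 1 − (1 − p)^N

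| N | Basis | Expected | Chance of at least one |
|---|---|---|---|
| 60 | 30 per arm | 0.03 | 3.0% |
| 100 | 50 per arm (the cap) | 0.05 | 4.9% |
| 150 | cap plus 50 screen failures (assumed) | 0.075 | 7.2% |
| 200 | cap plus 100 screen failures (assumed) | 0.10 | 9.5% |

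The documents give neither the number of screen failures nor the share of children whose MRI is clinical. Every clinical scan reused lowers these figures.

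**The case against.** The strongest reply is that the protocol already handles this. Section 6.1.3 is a rule written for the pre-enrollment period and takes study-procedure findings out of medical history. Section 8.6 requires their assessment without limiting when, and 8.4 asks sites to seek AEs at each contact. A careful site would capture the event. That stands as far as it goes: such harm *can* go ungraded, not that it must. It does not remove the contradiction, because 8.3 sits in the safety chapter, where a site looks for the rule, and the schedule agrees with it.

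A reader might infer that the events vanish and that the DSMB has no view of them. The documents do not support this. Medical history is entered in the eCRF (6.1), screen failures are tracked and documented (4.5), and DSMB tables cover screen failures and anything else the Board requests (8.13). The event would be misclassified and ungraded, not erased. However, nothing says that those tables would show procedure-related harm.

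A reader might also infer that mild effects are lost because AE collection starts late. Step 3 shows otherwise: the 8.8 threshold excludes them at any time.

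Finally, not every child is exposed, because a clinical MRI may be reused. That is correct and limits the size. It leaves the rule itself unreconciled, and the rule also governs other screening procedures done for research, such as blood draws or a sedated echocardiogram.

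**Conclusion.** The concern holds as an internal contradiction with a consequence for safety capture. Section 8.3 and note 8 conflict with 6.1.3 and 8.6, and 7.2 leaves screen failures outside the safety analysis whichever section a site follows. It affects no efficacy endpoint, power statement or treatment comparison.

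In number, serious events should be few: at most 0.05 expected in 100 scans, assuming that every scan is research-only and that the protocol's general pediatric bound applies. A reader might argue that single-ventricle infants face a much higher anesthesia risk and that several serious events would be missed. The documents give no rate for this population, so no such count can be supported. The case for acting rests on the conflicting rules and the missing route for reporting, not on frequency. It should be corrected because the correction is simple and concerns harm that the research itself may cause.

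**What to change.** 1. Carry the 6.1.3 exception into both paragraphs of 8.3, and amend schedule note 8 and 6.2.1 to match.
2. State that from consent, AEs related to study-required tests or procedures (MRI, anesthesia or sedation for study imaging, intravenous access, study blood draws) that meet the 8.8 threshold go on the AE eCRF, with severity, seriousness and causality assessed and 24-hour SAE reporting applied.
3. Decide whether mild procedure-related events are wanted. If so, add relatedness to study-required procedures as a trigger in 8.8, so that one threshold applies before and after enrollment.
4. In 7.2 and 8.13, provide a separate listing of these events for the DSMB covering all consented children, including screen failures, and keep it apart from the post-enrollment comparison of arms.

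The cost is protocol wording, opening the existing AE form at consent, and slight extra data entry at sites. The comparative safety analysis is unchanged.
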